In this 3-arm randomized controlled trial (RCT), parent-child dyads will be assigned to a 10-week group-based intervention, delivered to parents, targeting adolescent substance use prevention and diet improvement through parenting and family-focused strategies. The proposed study will be conducted in partnership with our longtime research collaborator, the ADA. ADA has a demonstrated record of successfully recruiting and retaining thousands of Mexican heritage and other Latino parents into *Realizing the American Dream* (RAD), their academic success program with no substance use prevention or nutrition content. ADA's trained community facilitators will lead the parents' groups (15 parents per group) via three conditions: substance use prevention and healthy nutrition (FPNG+; n=498 parent-child dyads); substance use prevention only (FPNG; n=498 parent-child dyads), or a comparison condition (RAD; n=498 parent-child dyads). The three curricula will be delivered through ADA programming, offered to families of 6th – 8th grade students (11-14 years old) in 18 different schools (6 per condition). Randomization will occur at the school level, each school randomly assigned to one of the three conditions. Participants will be consented for the specific condition their school is randomized to (i.e. the consenting materials will only describe the condition the school is assigned to).

Participant recruitment

We will recruit parent-child dyads consisting of one parent and one youth enrolled in 6th, 7th or 8th grade. Following inclusiveness policies from our community partner, the American Dream Academy (ADA), parents of children enrolled in other grades will also be included if interested in the program, but their children will not be part of the study. Inclusion criteria are as follows:

Youth:

- ages 11-14
- enrolled in 6th-8th grade at the time of recruitment from the ADA programs

Adults:

- age 18 or older
- parent/caregiver/guardian of an eligible youth or parent of a child enrolled in participating schools who expresses interest in the program

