Power calculations considered design effects related to the clustering of outcome means by school sites. The total estimated sample size is 1494 parent-child dyads, across 18 schools. Based on data from the FPNG effectiveness trial, the level of clustering is low for our outcomes, including an intraclass correlation equal to 0.01, a student level R-square of 0.25, and a school level R-square of 0.03.² Because the effect size for substance use outcomes ($d=0.20$; FPNG vs. C) is lower than the expected effect size for nutrition outcomes ($d=0.78$; prior non-related intervention study), the total sample size is calculated for substance use outcomes. Accounting for these parameters, the power of this design is 0.802. For the subsample, the estimated sample size is 126 households across 18 schools – 7 per school. The average effect size of .69 is calculated based upon prior work on home food availability of vegetables, fruits, and desserts. Given the above stated parameters, the power of this design is 0.814.

All analyses will be conducted using multilevel analyses in Mplus,²⁷ with families clustered within schools. This analysis accounts for the clustering which, if uncorrected, may result in biased standard errors.²⁸ All analyses will employ a robust maximum likelihood estimator to adjust for any non-normality in the distributions of outcomes and to best control for Type I errors.²⁹ The analyses will also utilize full-information maximum likelihood (FIML)³⁰ to conduct intent-to-treat analyses that account and adjust for attrition and any item missing data.

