We will use both baseline adjusted general linear model procedures (i.e., variants of multiple regression) and latent change modeling to test intervention efficacy. In all models, because the FPNG Plus is the intervention condition of interest, all analyses will use FPNG Plus as the reference group. The two remaining conditions (FPNG and Comparison) will be compared with the reference group. The first method will predict short-term (T2) and then long-term (T3) post-test outcome measures (e.g., adolescents substance use and diet outcomes), while controlling simultaneously for the baseline (T1) measure of the particular outcome. Latent-change models³¹ will test whether and how changes over time in the outcomes differ significantly. Latent-change models will enable the assessment of change between T1 and T2 separately from change between T2 and T3. This examination will simultaneously test for improvements manifested during the course of the intervention (i.e., between T1 and T2) and for improvements maintained following the completion of the intervention (i.e., between T2 and T3). For mediation analyses, we will employ multivariate linear regression path analyses.^{32,33} Each mediation model will test the indirect path between the intervention condition at T1 and outcome measures at T3 (e.g., adolescents substance use and nutrition outcomes) mediated through family functioning, parenting strategies, and parents' social support at T2. Mediation models will control for baseline (T1) measures of the particular mediator and outcome. We will employ a bias-corrected bootstrap approach to test the indirect effect.³⁴

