The moderation effects of sociocultural factors on outcome measures will be tested employing mean centered interactions of the measures of acculturation, acculturative stress, food insecurity, and resiliency with the dummy variable contrasts of intervention conditions, following Aiken & West (1991).³⁵ We will use baseline adjusted general linear model procedures to test for moderation. If significant moderation exists, we will use latent-change models to test whether and how changes over time in the outcomes differ significantly between adolescents who vary in the sociocultural moderating measures of interest (e.g., for those adolescents who are less and more acculturated). Intervention effects on cardiometabolic risk factors and home food environment outcomes measured in the subsample will be tested through baseline adjusted regression models, including models that can appropriately analyze count data (e.g., Poisson, Negative Binomial). We will examine changes in short-term (T2) and long-term (T3) outcomes with dummy variable contrasts of intervention conditions, while controlling simultaneously for the baseline (T1) measure of the particular outcome.

References

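### With 6 schools per arm and no small-sample correction stated, the planned robust standard errors would, if used uncorrected, give baseline-adjusted T2 and T3 contrasts a Type I error of about 7–10% instead of 5%

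*Combined protocol and SAP*

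**What the plan says.** The Study design section fixes the unit of randomisation: "Randomization will occur at the school level, each school randomly assigned to one of the three conditions". The curricula are offered "in 18 different schools (6 per condition").

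The Data Analysis Plan then makes these commitments:

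- **Model and estimator.** All analyses are multilevel, in Mplus, with families nested in schools. They will "employ a robust maximum likelihood estimator to adjust for any non-normality in the distributions of outcomes and to best control for Type I errors". FIML is used "to conduct intent-to-treat analyses that account and adjust for attrition and any item missing data".
- **Efficacy tests.** "We will use both baseline adjusted general linear model procedures (i.e., variants of multiple regression) and latent change modeling to test intervention efficacy". The first of these two routes predicts T2 and then T3 outcomes adjusted for T1.
- **Contrasts.** FPNG+ is the reference arm, and "The two remaining conditions (FPNG and Comparison) will be compared with the reference group".
- **Subsample.** Cardiometabolic and home-food outcomes use baseline-adjusted regressions, "including models that can appropriately analyze count data (e.g., Poisson, Negative Binomial").
- **Power.** "Accounting for these parameters, the power of this design is 0.802".

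The plan names no alpha, sidedness, test statistic, degrees of freedom, reference distribution or small-sample correction for the condition contrasts. The one special inference method it names, the bias-corrected bootstrap, is for the mediation indirect effect only.

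**The concern.** Condition varies only between schools, so the information about the precision of a contrast comes from the spread among schools, not from the 1494 dyads. With 6 schools per arm that spread is poorly estimated, and an uncorrected sandwich variance is also biased downward. The plan offers the robust estimator as its Type I error safeguard. Robustness to non-normality does not address a small number of schools, and here the uncorrected robust variance makes control worse.

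The error at stake is declaring FPNG+ different from FPNG or from the comparison condition when their effects are equal. P-values would be too small and confidence intervals too narrow, for both contrasts, at T2 and T3, for each outcome tested this way.

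**Working it through.** **Inputs from the documents.** 18 schools, 6 per arm; 1494/18 = 83 dyads per school; ICC 0.01; R-square 0.25 (student) and 0.03 (school); d = 0.20; 126/18 = 7 households per school in the subsample.

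**Assumptions.** A nominal 5% level, because the plan states none. Sidedness and reference distribution are varied. School sizes are equal unless noted.

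**1. The plan's own figure.** The variance of an adjusted school mean is 0.01×0.97 + 0.99×0.75/83 = 0.0097 + 0.0089 = 0.0186. The standard error of a 6-versus-6 contrast is sqrt(2×0.0186/6) = 0.0788, and d/SE = 2.54. Two-sided 5% power with a normal reference is 0.718. A one-sided 5% normal test gives 0.814, near the stated 0.802, but other readings come as close (all 18 schools as one two-group comparison at alpha 0.025 gives 0.807). The stated power therefore does not reveal which test is planned.

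**2. Bias of the robust variance.** In the balanced case the uncorrected sandwich takes each arm's sum of 6 squared school residuals and divides by 6 where 5 is unbiased. The variance is 5/6 of its proper size and the standard error is sqrt(5/6) = 0.913 of it. The ICC does not enter this factor.

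**3. Size of the test, closed form.** Two-sided size = P(|t10| > c×sqrt(5/6)), where c is the critical value used.

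| Reference | c | c×0.913 | Uncorrected robust | With an 18/17 factor (variance 15/17) |
|---|---|---|---|---|
| normal | 1.960 | 1.789 | 10.4% | 9.5% |
| t15 | 2.131 | 1.946 | 8.0% | 7.3% |
| t10 | 2.228 | 2.034 | 6.9% | 6.3% |

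So a nominal 95% interval would cover about 90% (normal) to 93% (t10). One-sided at 5%, the robust variance gives 8.2% (normal) and 6.5% (t10); the 18/17 factor lowers these to 7.7% and 6.0%. Changing only the reference to t does not remove the excess, because the variance itself remains too small.

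**4. Simulation with T1 in the model**, at the stated inputs. Two separate simulations of null trials gave, for the uncorrected robust variance, 10.6% and 10.7% (normal), 8.2% and 8.3% (t15), 7.1% and 7.0% (t10).

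**5. Departures from the balanced case, robust variance.**
- Unequal school sizes (assumed CV 0.5): normal reference 11.1% and 12.5% in two runs; 11.5% with skewed errors as well.
- ICC of zero, 83 per school: 10.7% (normal), 7.1% (t10).
- Linear model, 7 per school: 10.5% (normal), 7.0% (t10).
- Count outcomes, 7 per school, 27 assumed settings (mean 2 to 10, dispersion 0.25 to 1, school SD 0 to 0.3 on the log scale): 10.2–11.8% (normal), 6.8–8.1% (t10).

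**6. Model-based ML, for comparison.** Here the variance is pooled over 18 schools: P(|t15| > c×sqrt(15/18)) = 9.4% (normal) and 7.1% (t15). Simulation at ICC 0.01 and 83 per school gave 9.0–9.5% and 6.7–6.9%. The excess is gone when the ICC is zero (4.6% with a normal reference) and nearly so at 7 per school (5.7% normal, 3.9% t15), because the school variance is then often estimated as zero.

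**7. Corrected tests.** At the stated inputs with equal schools, REML with 15 df gave 5.0%, and the sandwich multiplied by 6/5 with t10 gave 5.1–5.3%. With unequal schools (CV 0.5) the fixed 6/5 factor gave 6.4% in one simulation and 4.9–6.3% in another, depending on weighting (up to 7.5% at CV 0.7). A pooled school-level t-test on 15 df gave 5.1% at CV 0.5. With assumed missingness (about 15% of T1, 16% of T2) and multiple imputation including school, REML with 15 df gave 4.2%.

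**The case against.** The strongest reply is that the plan names an estimator and a program, not a variance formula or reference distribution. The analysts may apply a correction that they did not write down, so no error rate can be read off the documents. This stands, and every rate above is conditional on the robust variance being used uncorrected. A reader might infer that the trial's Type I error is 10%, or double nominal. The documents do not support that: the near-doubling needs a two-sided normal test, while other references in the equal-size closed form give roughly 1.2 to 1.6 times nominal.

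A second reply is that the plan's own ICC is only 0.01. For model-based ML this has force, since its inflation disappears near zero ICC and largely so at 7 per school. For the robust variance, which the plan names, it has none, because the 5/6 factor depends on the number of schools. Even at ICC 0.01 the school component is 0.0097 of 0.0186, or 52%, of the variance of a school mean.

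Third, the baseline-adjusted models are one of two planned efficacy routes. A reader might extend the figures to the latent-change, mediation or moderation models. Those were not assessed, and nothing here establishes a rate for them.

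Finally, the remedy has limits. A fixed 6/5 rescaling with 10 df is not reliably at 5% when schools differ in size, which is likely with volunteer recruitment. REML with 15 df was checked only in the main sample; at 7 per school it was conservative in one check (about 3.2%).

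**Conclusion.** The point holds in conditional form. Each baseline-adjusted T2 or T3 contrast rests on 6 versus 6 schools, and the plan relies on a robust estimator for Type I error control without a correction for that number. Used uncorrected, at a nominal two-sided 5% and with equal school sizes, the error would be about 10% (normal), 8% (t15) or 7% (t10), and about 6–8% one-sided. With a normal reference it would be about 11–12% when school sizes vary (assumed CV 0.5), and 10–12% for subsample counts under the assumed settings. Model-based ML inflation of about 9% (normal) or 7% (t15) applies only to the main sample at ICC 0.01.

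The difference between 0.72 and the stated power of 0.802 might be read as a consequence of this problem. It is not: 0.72 already assumes a known variance, so that gap is a separate matter and lends no weight here.

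**What to change.** 1. State alpha, sidedness and the reference distribution for the condition contrasts.
2. Base the main-sample T2 and T3 contrasts on REML with Kenward-Roger or Satterthwaite degrees of freedom, computed from the data and not fixed at 15. Model T1 jointly with the outcome, or multiply impute with school in the imputation model, so that families with a missing T1 stay in and the handling matches FIML.
3. Alternatively, use a leverage-based bias-corrected sandwich (not a fixed 6/5 factor) with Satterthwaite-type t degrees of freedom, or a school-level permutation test that follows the actual allocation. Twelve schools split 6 and 6 give 12!/(6!×6!) = 924 arrangements, enough for a 5% test.
4. For the subsample, including count outcomes, use the leverage-corrected sandwich with t or the permutation test.
5. Mplus robust ML with FIML may stay for the path and latent-change models.

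**Cost.** Plan wording and one added analysis routine; randomisation and data collection do not change. Intervals become wider than uncorrected robust normal intervals by sqrt(6/5)×2.131/1.96 = 1.19 (15 df) to sqrt(6/5)×2.228/1.96 = 1.25 (10 df), that is 19–25% with equal schools. Two-sided pairwise power at d = 0.20 is 0.66 (15 df) or 0.63 (10 df) against 0.72 for a known-variance normal test, a loss of about 6–9 points.

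### As specified, the T3 baseline-adjusted regressions make no use of T2 data from families lost after T2, so for these models FIML adjusts for attrition only if dropout is unrelated to T2 given T1 and arm

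*Combined protocol and SAP*

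**What the plan says.** All references are to the Data Analysis Plan section of the combined protocol and SAP.

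- **Missing data.** FIML is applied to the analyses in general "to conduct intent-to-treat analyses that account and adjust for attrition and any item missing data". The section gives no expected dropout rate, auxiliary variables, assumed dropout mechanism or missing-data sensitivity analysis.
- **First efficacy method.** "The first method will predict short-term (T2) and then long-term (T3) post-test outcome measures", "while controlling simultaneously for the baseline (T1) measure of the particular outcome". T2 is not named as a variable in the T3 model.
- **Second efficacy method.** "Latent-change models will enable the assessment of change between T1 and T2 separately from change between T2 and T3". All three visits are in this model.
- **Status.** The plan uses both methods ("We will use both baseline adjusted general linear model procedures", together with latent-change modelling) and names neither as primary.
- **Moderation.** "We will use baseline adjusted general linear model procedures to test for moderation". Latent-change models follow only if moderation is significant.
- **Subsample outcomes.** Cardiometabolic and home food outcomes "will be tested through baseline adjusted regression models, including models that can appropriately analyze count data". No latent-change model is planned for them.
- **Mediation.** T2 mediators are in the model, but the outcome is adjusted for its T1 value only: "Mediation models will control for baseline (T1) measures of the particular mediator and outcome".

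**The concern.** FIML draws information only from variables that are in the fitted model. In a regression of T3 on condition and T1, a family without T3 has no outcome to contribute, so its T2 response is unused. Maximum likelihood then gives the same T3 contrast as an analysis of families with T3 observed, conditional on T1 and arm. That is valid only if, given T1 and arm, leaving after T2 is unrelated to what happened at T2.

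The T2 response is a natural predictor of both T3 and dropout. The relation could also differ by arm: the three curricula differ, and families are consented knowing only their own school's condition. If it does differ, the long-term contrast between FPNG+ and another arm is biased, although the data that would remove the bias under missing at random have been collected.

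**Working it through.** **What the plan offers to reproduce.** It gives no dropout or attrition figure. The only nearby figure is the power of 0.802, which is relevant here only as a source for a clustered standard error. For a pairwise comparison of 6 v 6 schools with 83 dyads each (1494/18):

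Var = 2 × [ICC(1 − R²school)/J + (1 − ICC)(1 − R²student)/(J × n)]

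= 2 × [0.01 × 0.97/6 + 0.99 × 0.75/498] = 0.00622, so SE = 0.079.

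With d = 0.20 and two-sided 5% normal testing, power is 0.718. Treating the 18 schools as two arms of nine gives 0.831 (t reference). Alpha and sidedness are not stated, so whether 0.802 can be reproduced is undetermined. Nothing below depends on it.

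**Inputs for the bias.** From the plan: d = 0.20, ICC 0.01, R-squares 0.25 and 0.03, 6 schools per condition. Assumed: correlations T1-T2 0.5, T2-T3 0.6, T1-T3 0.5 (0.5 is the square root of the student R-square of 0.25, if that R-square reflects the baseline measure); dropout after T2 of 10-20%; log-odds of dropout rising by b = 0.5 to 0.8 per SD of worse T2; normal outcomes; complete T1. Outcomes are scaled so that higher is better.

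**Closed-form approximation.** Given T1, the slope of T3 on T2 is (0.6 − 0.5 × 0.5)/(1 − 0.5²) = 0.35/0.75. The variance of T2 given T1 is 0.75. If a proportion p drops out with slope b, the T2 residual mean among those who stay shifts by about b × p × 0.75. The bias in the T3 contrast is therefore about

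(0.35/0.75) × 0.75 × p × (b in FPNG+ − b in the other arm) = 0.35 × p × (difference in b).

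**Results with no true effect,** beside large unclustered simulations (mostly 2,000,000 subjects per scenario):

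| Slope b, FPNG+ / other arm | Dropout | Closed form | T3 on T1 and condition, simulated |
|---|---|---|---|
| 0.8 / 0.8 | 20% | 0 | 0.003 |
| 0.8 / 0.5 | 10% | 0.35 × 0.1 × 0.3 = 0.011 | 0.009 |
| 0.8 / 0.5 | 20% | 0.35 × 0.2 × 0.3 = 0.021 | 0.017 |
| 0.5 / 0 | 10% | 0.35 × 0.1 × 0.5 = 0.018 | 0.016 |
| 0.8 / 0 | 10% | 0.35 × 0.1 × 0.8 = 0.028 | 0.027 |
| 0.5 / 0 | 20% | 0.35 × 0.2 × 0.5 = 0.035 | 0.035 |
| 0.8 / 0 | 20% | 0.35 × 0.2 × 0.8 = 0.056 | 0.052 |

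A joint likelihood for T2 and T3 given T1 and condition recovers the true value to within about 0.003.

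**With a true effect of 0.20.** Dependence in FPNG+ only gives 0.22-0.25 from the T1-only model. Dependence in the other arm only gives 0.15-0.18. The joint model gives 0.20.

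**Against the planning effect and the precision.** The one-arm range of 0.016-0.052 is 8-26% of 0.20. With 20% dropout, n = 66.4 per school and SE = √{2 × [0.0097/6 + 0.7425/398.4]} = 0.083. The largest value is 0.052/0.083, or about 0.6 SE.

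**Outer range.** With T2-T3 correlation 0.4-0.8, dropout 10-30% and slopes 0.5-1, a true effect of −0.20 is estimated as −0.18 to −0.20 when the dependence is equal across arms, and as −0.05 to −0.34 when it is confined to one arm.

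**The case against.** **The latent-change models already use T2.** This stands for the main survey outcomes. The FIML sentence covers those models too, and under missing at random families lost after T2 contribute there; the T1-T3 contrast is the sum of the two segments. A reader might infer that the attrition statement is wrong for the whole plan; the documents do not support that. But the T3 regression is an efficacy test of equal standing, and there is no rule for the case where the two methods disagree. Nor does the objection reach the subsample outcomes, or moderation that is not significant at the first step.

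**Silence is not exclusion.** A reader might infer that FIML cannot use T2 here. It can, if T2 is an auxiliary variable or a second outcome, and the plan does not rule this out. The supportable statement is that the models as specified do not do so.

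**Dropout that depends on T2 does not by itself bias the contrast.** This stands. With the same relation in every arm the bias is about nil under the main assumptions and at most about 0.02 in the wider range. A reader might also infer that the effect of FPNG+ would be overstated; the direction depends on which arm's dropout is the more selective.

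**The largest values rest on an extreme contrast.** Dependence in one arm and none in the other is a bounding case, and no dropout rate, slope or inter-visit correlation comes from the documents. Even there the bias stays below one clustered standard error under the main assumptions.

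**Conclusion.** The point holds as a gap between a stated property and a specified model. For the T3 baseline-adjusted regressions, the adjustment for attrition requires that dropout be unrelated to T2 given T1 and arm, which the plan neither states nor examines. The gap matters most for the subsample outcomes and the first-step moderation tests.

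Under the main assumptions the bias runs from about nil (same mechanism in all arms), through 0.01-0.02 SD (moderately different), to 0.02-0.05 SD in either direction (one arm only), at most about 0.6 of a clustered SE of 0.083. These sizes rest on assumed correlations, dropout rates and slopes, normal outcomes, complete T1, and simulations without clustering. They show what could happen; they do not show that the trial's T3 results are biased. It is a worthwhile, low-cost improvement to the plan.

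**What to change.** State in the Data Analysis Plan:

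- **Continuous outcomes.** Every T3 baseline-adjusted model, including the first-step moderation models, carries the T2 value of the outcome as an auxiliary (saturated-correlate) variable, or fits T2 and T3 jointly on condition and T1. T2 should not enter as a covariate, because that would remove the part of the effect that passes through T2.
- **Count outcomes in the subsample.** For Poisson or negative binomial models, use a joint model or multiple imputation that includes T2. Saturated correlates work through residual covariances, which these models lack.

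The T2 data are already planned. For continuous outcomes the cost is a sentence in the plan and a small change to the model code. For count outcomes it is somewhat more work. Joint two-level models also add school-level parameters with only 18 schools. Any gain in precision is small: in one unclustered check at n = 996 and 20% dropout the SE fell from 0.0613 to 0.0600, about 2%.

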Additional data will be gathered from a random subsample of self-identified Latino 126 families (42 per condition) at the same time points (T1, T2 and T3) to explore the preliminary effects of FPNG+ on modifiable chronic disease risk factors and the home food environment (see Measures). This data collection home visit is anticipated to last 90 minutes during which the following procedures will take place: (1) measurement of parent and child body weight, height, and blood pressure; (2) collection of a finger prick blood sample from parent and child for measurement of HbA1c and total cholesterol using portable point-of-care devices; (3) and completion of a home food inventory to record availability of fruit, vegetables, and sugar-laden foods. Because blood will be collected from a finger prick, we will only collect the necessary amount of blood to perform the proposed analysis (three to four drops) on site by using it directly into the measuring device (similar to glucometers used by patients with diabetes). The reactive strips used with the measurement instruments will be discarded immediately after they are used. No blood samples will be stored. The 24 hour Food Recall questionnaire will be done over the phone for both parents and youth. As part of the 24 hour Food Recall, parents will answer a short questionnaire regarding some of the food details that their child may not know, such as the type of oil they buy, what kind of fat they use for cooking, and the types of bread and milk they typically buy for the family.

Measures

Survey. Self-administered surveys will be available in Spanish and English so the respondent can complete it in the language he/she chooses without needing to request the accommodation. If participants cannot read in either language, a Research Assistant will read the questions to them. All constructs will be measured at all three time points (T1, T2 and T3) with the exception of sociodemographic characteristics.

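### The full-sample efficacy models adjust only for the outcome's own T1 value; a short fixed list of student-level baseline covariates already collected should be added

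*Combined protocol and SAP*

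**What the plan says.** **Adjustment.** The Data Analysis Plan gives two efficacy methods. The first regresses the T2 and then the T3 outcome on condition "while controlling simultaneously for the baseline (T1) measure of the particular outcome". The second is latent-change modelling: "Latent-change models will enable the assessment of change between T1 and T2 separately from change between T2 and T3". No covariates are named for it. FPNG+ is the reference group, and "The two remaining conditions (FPNG and Comparison) will be compared with the reference group". Mediation models add the T1 mediator. Moderation models bring in acculturation, acculturative stress, food insecurity and resiliency as interactions. Grade, sex and sociodemographics appear in none of these models.

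**Data available.** Grade (6th to 8th) and age (11 to 14) are eligibility items under Participant recruitment. Under Measures, Survey, all constructs are collected at all three times "with the exception of sociodemographic characteristics", so sociodemographics are collected, though the items are not listed. Sex is mentioned only for BMI percentiles, which belong to the home-visit subsample.

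**Design.** Under Study design, "Randomization will occur at the school level, each school randomly assigned to one of the three conditions". There are 18 schools, 6 per condition, and no stratification or matching is stated. Under Participant recruitment, call-centre scripts follow each site's assignment, and consent materials describe only the school's own condition.

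**Power inputs.** "The total estimated sample size is 1494 parent-child dyads, across 18 schools", with an intraclass correlation of 0.01, "a student level R-square of 0.25, and a school level R-square of 0.03", d=0.20 for substance use, and stated power of 0.802.

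**The concern.** Each planned contrast compares 6 schools with 6. With so few clusters and no stratification stated, chance differences in grade mix or family background between arms are likely. Recruitment adds a second route. Families join knowing which programme their school offers, and a programme on substance use and nutrition may attract different families from one on academic success. Randomising schools does not protect against that.

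It is reasonable to expect substance use to vary with age across grades 6 to 8. The T1 value of the outcome carries part of that, but it may carry little if recent use at T1 is close to zero for most youth. That is an assumption, since no prevalence is given. Any remaining imbalance in grade or background then passes into the estimate, although the data to reduce it are in hand. Some precision is also left unused.

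**Working it through.** **Inputs from the documents.** 498 dyads per arm and 6 schools per arm, so 498/6 = 83 per school; ICC 0.01; R-square 0.25 (student) and 0.03 (school); d = 0.20 with SD 1.

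**Assumed.** Alpha 0.05 two-sided (neither level nor sidedness is stated); no dropout (no rate is stated); noncentral t with 10 df for 12 schools in two arms.

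**Formula.** Per-school variance V = ICC(1 − R²_school) + (1 − ICC)(1 − R²_student)/83. Contrast variance = V(1/6 + 1/6).

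**Step 1: the plan's own figure.** V = 0.01 × 0.97 + 0.99 × 0.75/83 = 0.00970 + 0.00895 = 0.01865. Contrast variance = 0.01865/3 = 0.00622, SE 0.0788, noncentrality 0.20/0.0788 = 2.54. Power is 0.629 (t, 10 df), 0.660 (t, 15 df) or 0.718 (normal). The stated 0.802 is not reached for this contrast. Values within two points of it come only from settings the plan does not state: one-sided 0.05 with a normal reference (0.814), or 6 v 12 schools, two-sided, 16 df (0.785). The comparisons below start from 0.629.

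**Step 2: where the variance lies.** With both R-squares at zero, V = 0.01 + 0.99/83 = 0.02193. The stated R-squares remove 1 − 0.01865/0.02193 = 15%. Of what remains, 0.00970/0.01865 = 52% is between schools and 48% is within schools. Student covariates act mainly on the 48%.

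**Step 3: adding student-level covariates.** The documents give no R-square for them, so gains of 0.05 and 0.10 are assumed.

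| Student R² | V | Fall in variance | Power, t 10 df | Power, normal |
|---|---|---|---|---|
| 0.25 (plan) | 0.01865 | – | 0.629 | 0.718 |
| 0.30 (assumed) | 0.01805 | 3.2% | 0.643 | 0.732 |
| 0.35 (assumed) | 0.01745 | 6.4% | 0.658 | 0.746 |

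The gain is 1 to 3 points of power, with no school-level degree of freedom spent.

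**Step 4: the school mean of T1 as a further covariate.** It costs one school-level df. If it explains nothing more (school R-square stays 0.03), power falls from 0.629 to 0.619 (9 df). It breaks even at a school R-square of about 0.075. The documents give no value showing that it would get there.

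**Step 5: imbalance.** Bias from an imbalanced factor is the between-arm difference in that factor times its association with the outcome given T1. Neither is in the documents, so no figure can be given.

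**The case against.** The best defence is that adjusting for the baseline outcome in a multilevel model is coherent and parsimonious, and that T1 of the same outcome is usually the strongest prognostic variable. It already corrects at least part of any imbalance, and the latent-change models also represent T1 explicitly. The extra covariates buy only a few points of power under assumed gains, and more parameters are unwelcome with 18 schools. Much of this stands: the gain in precision is modest, and the list must be short. It does not answer imbalance in grade or background that T1 does not carry. Leaving further covariates unspecified also leaves room to choose adjustments after seeing results, across many outcomes, two time points and two model types.

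Three stronger readings are tempting, and the documents do not support them.

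- *That T1 adjustment explains only 3% of school variance, so the omitted covariates would recover most of the rest.* The plan attributes its R-squares to the earlier FPNG trial and does not say which covariates produced them. No R-square is given for the omitted ones.
- *That recruitment imbalance is wholly uncorrected.* T1 adjustment corrects part of it.
- *That the school mean of T1 should be required.* It is a trade-off of unknown benefit and can lower power. The plan is also silent on whether T1 is split into within-school and between-school parts, so a between-school term is not excluded.

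**Conclusion.** The point holds in a limited form. The full-sample efficacy models name only the outcome's own T1 value, while grade and sociodemographics are collected and unused in those models. With 6 schools per arm, no stated stratification and recruitment that follows allocation, imbalance in those measured factors beyond what T1 carries reaches the estimate. Its size cannot be computed from the documents. The loss of precision is small: power of about 0.63 against 0.64 to 0.66. That range rests on an assumed two-sided 0.05, 10 df, no dropout and an assumed rise of 0.05 to 0.10 in student R-square. The change is worth making because it is nearly free and limits later discretion; the planned analysis is not invalid without it. A covariate list does not repair selection on unmeasured factors, and the report should not claim that it does.

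**What to change.** Before unblinded analysis, add one short fixed list of student-level baseline covariates to the SAP: youth grade, sex if the survey records it for the full sample, and one or two sociodemographic items that the survey collects at baseline. Name the items, since the documents do not list them. Apply the same list to the full-sample T2 and T3 baseline-adjusted models and to the latent-change models. It need not extend to the subsample models, which rest on 126 households.

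Do not require the school mean of T1.

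The cost is SAP wording and no new data collection. The models gain a few parameters, and the SAP must say how missing covariate values are handled, because full-information maximum likelihood may need the covariates to be modelled as well. No school-level degree of freedom is spent.
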